6. There were significant concerns about the TINY¹ kit including:
 - The presumed large volume of blood required to process the sample.
 - Many people having a fear of needles.
 - Presumed difficulty in using the kit
 - Fear of contamination of the vial.
 - Fears about contaminating others.
7. For those familiar with SSKs, the oral swab was identified as an easier alternative to the use of the TINY kit. There were mixed views about the Dried Blood Spot kit as an alternative to the TINY kit.
8. Provider initiated targeting for offering HIV testing was understood as more likely to succeed than a patient initiated approach. However, consideration of the actual locations in which targeting conversations could take place was perceived as a vital component of the intervention.
9. It was regarded as very important that targeting conversations were initiated sensitively and the content of such conversations were considered in detail in order to avoid perceptions of racism.
10. Provider-initiated targeting which used appearance alone was generally understood as unacceptable. Targeting which addressed more detailed issues such as country of origin or national identity were understood as more acceptable however, they could still be understood as problematic.
11. Tailoring the intervention for individual circumstances was understood as reducing the key barriers of perceived racism and discrimination.
12. For service delivery, it would be better if personal details were not collected at the point of kit collection from a service provider however it was acceptable to have these collected for the purpose of a study and by a trusted professional.
13. It is acceptable for participants to receive a non-reactive result via text message.
14. It is acceptable for the standard NHS clinical governance mechanisms for HIV result management to be used for the study.

¹ TINY kit requires collection of a few drops of blood (obtained by pricking a finger with the supplied lancet) in a small collection vial. The test enables the specimen to be transported to a lab, by post, in a vial that contains preservatives, which stabilize the sample for up to 21 days if temperatures are between 4° C and 37° C.

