Despite the absence of a CE marked assay for saliva HIV testing, on 22nd May 2015 there was a call for expressions of interest in a national self-sampling tender from Public Health England. The call specifically included online distribution of a choice of saliva or blood-based self-sampling for HIV. Formal invitations to tender were issued on 28th July which again included preference for inclusion of a saliva-based option however on the 18th August some clarification on the national tender process were issued. These included the following statement.

“UK national standards (BHIVA 2008) set 4th Generation HIV as their standard. See <http://www.bhiva.org/documents/guidelines/testing/glineshivtest08.pdf>

The commissioning parties entering into this wish to adhere to this standard.

The recommended first-line assay is one which tests for HIV antibody AND p24 antigen simultaneously. These are termed fourth generation assays, and have the advantage of reducing the time between infection and testing HIV positive to one month which is one to two weeks earlier than with sensitive third generation (antibody only detection) assays.

In any event CE marked methods are required in the delivery of this service. Whilst this may restrict the range of home sampling methods that can be used during the initial period of delivery, it gives the provider opportunities to offer other methods, during the life of the contract, as other CE marked products become available.

There is no preferred test kit supplier or manufacturer.”

Thus despite the Orasure SSK being preferred by both service providers and users, University College London Hospitals NHS Foundation Trust (UCLH) and the processing laboratory (The Doctors Laboratory) felt unable to offer a saliva based SSK option and advised we use the CE approved, fourth generation TINY vial. The full intervention is described in section 6.4. In brief, the intervention involves using a designed script to opportunistically offer an HIV SSK to Black African service users during routine engagement with primary care and with services provided by community based organisations. The intervention will be provided by two types of distributors:

- **GP Practice:** Practice Nurses will offer the intervention.

- **Community Based Organisation:** Community workers will offer the intervention during routine outreach services.

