5.5 Secondary Outcome Measure

1. Point of delivery outcomes:
 - Acceptability of targeted HIV SSK distribution, including rationales for accepting or refusing the offer of an SSK
 - Acceptability and feasibility of targeted SSK distribution among specified service providers, including utility of protocols for SSK targeting, offers and intervention uptake.
2. Data collection outcomes:
 - Demonstration that intervention models and service provider training and support incorporates sufficient capacity to successfully record the numbers of: people offered SSK, accepting SSK, and returning SSK
 - Feasibility of collecting correct contact details enabling follow-up, reminders and communication of results
3. Pathway to care outcome measures:
 - Proportion of those whose samples are reactive who: a) are informed of results in person and b) who attend for confirmatory testing at an NHS setting of their choice
4. Overarching outcome measures:
 - Cost per person kit distributed and cost per HIV diagnosis per setting
 - Attrition rates and loss to follow up
 - Confirmatory testing, proportion of those receiving an HIV positive diagnoses, and clinical stage at diagnosis
 - Feasibility and sensitivity of outcome measures (testing, behavioural and economic) for a definitive trial.

6. Study Design

This is a prospective, mixed-methods, non-randomised study. The study evaluates the effectiveness of self-sampling for HIV as well as the cost effectiveness of distributing the SSK through GP settings and Community based organisations. Feasibility and acceptability will also be assessed through a process evaluation. Please see the fieldwork schematic diagram in section 6.1 for further information.

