6.7.2 Targeting and Recruiting

The distributor will aim to introduce and recruit eligible candidates to the research study. They will explain the benefits of participating and having an HIV. All distributors will answer questions and aim to alleviate any concerns participants may have. The script below initiates the recruitment process:

“We are currently involved in an important study that I wonder if you’d be interested in taking part in? We want to see if people will use HIV self-sampling kits. HIV treatments are so good now; that you can live a normal healthy life with HIV, and being on treatment also stops most people from passing on the infection. So we are trying to find new ways to offer testing as it’s the people who don’t know their HIV status who become unwell.

This study is looking at whether people from the Black African community would want to use these kits. It’s a great opportunity as most people don’t have access to them yet.

Testing is very easy. It's all in this kit, which you take home to use when it is convenient to you. Once you've collected the sample you put it in the envelope provided and pop it in the post.

A few days later you are contacted by a NHS health clinic via your mobile phone with the results. Most people testing will be negative. A few people will have a test suggesting they have HIV (this is called a 'reactive' test) and we would have to check the result is correct.

It's all completely private and confidential - no one, other than the clinic contacting you, will know your result unless you want them to. What do you think? Is this something that you may be willing to try?"

If answer = NO then go to section A

If answer = YES then go to section B

Section A

"That's absolutely fine. We would really like to understand why people do not want to participate in the study. On this card are some of the common reasons why people say no – "

(Hand participant card)

"Would you possibly be able to let me know if any of the numbers match with your own reason? And if so which numbers? Of course it is also ok if you do not want to give me a reason."

(Participant gives reason or declines to do so)

(If reason given then insert into participant screening and enrolment log)

(Contact ends)

Section B

"First we need to determine if you're eligible for the study. Are you aged 18 or older and do you consider yourself Black African?"

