Appendix 3 HAUS Study Participant Screening and Enrolment Log

Name of Person Screening and Enroling participants										
Site name and Address										
ID Number	Sex		Initials	Age (years)	Country of Birth	Screening Date (dd/mm/yy)	Enrolled?		Reason if not enrolled (insert number from list below) If Did Not Attend insert #11	Comments
	M	F					 Yes	 No		
							 Yes	 No		
							 Yes	 No		
							 Yes	 No		
							 Yes	 No		
							 Yes	 No		
							 Yes	 No		
							 Yes	 No		
							 Yes	 No		
							 Yes	 No		
							 Yes	 No		
							 Yes	 No		
							 Yes	 No		
1. Recently tested for HIV 2. Do not believe at risk of HIV 3. Prefer to test elsewhere 4. Prefer not to use a self-sampling kit 5. Prefer not to know HIV status 6. Do not like being offered an HIV test just because black African 7. Already knows is HIV positive 8. Prefer not to say 9. Other 10. Does not meet eligibility criteria 11. Did not attend										

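### The refusal codes have no category for blood, needle or finger-prick aversion, so the coded data cannot separate rejection of the blood kit from rejection of self-sampling

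*Protocol*

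**What the plan says.** Protocol section 5.5, item 1, makes acceptability of targeted distribution a secondary outcome, including "rationales for accepting or refusing the offer of an SSK".

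The reasons are collected in two steps. In the script in section 6.7.2 (Section A), a person who says no is handed a card of common reasons and asked: "Would you possibly be able to let me know if any of the numbers match with your own reason". The distributor then completes the log in Appendix 3, whose column reads "Reason if not enrolled (insert number from list below".

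The list has 11 entries. Those that matter here are:

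- code 3: "3. Prefer to test elsewhere"
- code 4, followed by code 5: "4. Prefer not to use a self-sampling kit 5. Prefer not to know HIV status"
- codes 8 and 9, followed by an administrative code: "8. Prefer not to say 9. Other 10. Does not meet eligibility criteria"

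The log also has a free-text comments column.

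On the device, section 4.2.1 (finding 6) lists significant Phase 1 concerns about the TINY kit: the blood volume, difficulty of use, contamination, and "Many people having a fear of needles". Finding 7 adds that people familiar with self-sampling saw the oral swab as easier. Section 4.2.3 explains that the blood vial was adopted for regulatory reasons: "Thus despite the Orasure SSK being preferred by both service providers and users".

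**The concern.** Phase II is meant to inform the intervention design for a possible phase III trial. If people decline, the designers need to know whether they object to taking their own sample at all or to pricking a finger and filling a vial. The first bears on the whole idea. The second bears on a component that section 4.2.3 shows was not the preferred one.

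The protocol had evidence of the blood-specific barrier before the list was fixed, but the list has no place for it. This is a matter of data capture at first contact. A later analysis plan cannot recover a reason that the form did not record.

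**Working it through.** No figure in the protocol bears on this point, so there is nothing to reproduce. The check is to set the form against the other sections.

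**1. Is there a code for the known barrier?** Going through codes 1 to 11 in Appendix 3, none mentions blood, needles, finger-prick or the vial. The list does not avoid Phase 1 barriers in general: code 6 covers objection to being offered a test because of ethnicity, which matches findings 9 and 10 in section 4.2.1. The intervention manual (Appendix 6, section 5.4) has a whole section of anticipated questions on blood-based testing, including fear of needles. The barrier was expected in conversation but not on the form.

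**2. Where would such a refusal be recorded?** Someone put off by the finger-prick could choose:

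- code 3, preferring a test elsewhere;
- code 4, not wanting this kind of kit;
- code 8, giving no reason;
- code 9, the residual code.

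Write n3, n4, n8 and n9 for the counts, taking one main reason per refuser and assuming these four codes are where blood aversion falls. Let B be the number who refused because of blood or needles. From the codes alone:

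0 ≤ B ≤ n3 + n4 + n8 + n9

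Within code 4 the blood-related share can be anything from 0% to 100%. Any free text that mentions blood raises the lower limit above zero. It does not supply the missing counts, because nothing asks for it.

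**3. Does another instrument reach refusers?**

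- Acceptability questionnaire: packed inside the kit (section 6.5.2) and describing kit users (section 6.8.1).
- Participant interviews: 10 non-returners + 20 returners = 30, all of whom agreed to take part (section 6.8.2).
- Weekly distributor log (Appendix 11): asks about the distributor's own experience and confidence, not refusal reasons.
- Distributor focus groups and logged support queries (section 6.11.3): second-hand or incidental, and not countable.

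**4. What does a refuser know about the sample?** The sections differ.

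- Section 6.7.2: the script asks for a yes or no without mentioning blood, lancet or vial. The information sheet comes after a yes.
- Section 6.7.1: interested people receive the information sheet to read, and a refusal at that stage is logged.
- Appendix 6, section 1.3: a demonstration of sampling comes before the person is asked whether they are willing.
- Section 6.7.5: the kit is explained after the baseline questionnaire, which follows consent.

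Under the first sequence an early refuser may not know that the sample is blood. Under the second and third they may. The log does not show which applied.

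**The case against.** The strongest reply is that the script in section 6.7.2 never mentions blood before the card is handed over. Someone who refuses there, with no other knowledge of the kit, is not refusing the blood device, and a new code would not change that. This stands for that sequence. It does not cover refusals after the information sheet (section 6.7.1) or after a demonstration (Appendix 6, section 1.3). It is also a reason to reconcile those sections as well as the codes.

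A second reply is that the form is not closed. It has a residual code and a comments column, the script presents the card as listing only some common reasons, and section 6.7.1 asks for as much information as the person will give. This also stands. A reader might infer that code 4 absorbs every blood-related refusal, or that the study can learn nothing about them. The documents support neither: blood has no code, so such refusals may scatter, and some may be written down.

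Third, device aversion is explored among people who accepted a kit. Appendix 5, item 7, asks how they felt about taking the sample and why, and the interview guide (Appendix 12) probes kit characteristics. That helps a mixed-methods study, but it describes acceptors and not the people whose refusal is the outcome.

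A reader might also infer that a high code 4 count would be taken as proof that self-sampling is unacceptable, or that section 4.2.3 promises another device for phase III. The protocol says neither. It documents the concerns about TINY openly, and the remark about future CE-marked methods belongs to a national tender.

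**Conclusion.** The point holds for the coded data. The list omits a barrier that the study's own Phase 1 had identified, and the coded refusal reasons cannot separate rejection of the blood device from rejection of self-sampling.

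The number of people affected cannot be estimated, because the protocol gives no refusal rate and no expected distribution of reasons. All that can be said is that the blood-related share of code 4 is unidentified, from 0% to 100%, and that codes 3, 8 and 9 may hold further cases. This rests on two assumptions: that some refusers learn the sample is blood before they decline, and that distributors do not routinely write the reason in free text.

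The effect is confined to one component of a secondary outcome. The primary outcome (kit return) and the sample size are untouched. It is a cheap improvement to the form and not a flaw in the main design.

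**What to change.** On the card and in the Appendix 3 log:

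- Replace code 4 with two codes: *Do not want to prick finger / give blood* and *Do not want to self-sample by any method*.
- Require a short text entry whenever the residual code is used.
- Let the log hold more than one number. The script in section 6.7.2 already asks for numbers in the plural, while the log column asks for one.
- Report the two new codes separately by setting.

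If codes for difficulty in taking one's own sample, for posting or for accuracy are also added, report them as concerns about self-sampling in general. They would apply equally to a saliva kit. Section 4.2.1 (finding 1) lists transit security and accuracy as concerns about self-sampling, not about TINY.

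Reconcile the script in section 6.7.2 with sections 6.7.1 and 6.7.5 and with Appendix 6, section 1.3, so that it is clear what a person had been told about the sample when they declined.

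The cost is a revised card and log before recruitment starts, both slightly longer, and an edit to align the recruitment sections.

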Appendix 4: Baseline Questionnaire

Thank you for agreeing to be part of this study. Please complete the following information. The questionnaire is confidential and takes less than 5 minutes to fill in.

First Name _____

Surname _____

Affix Kit
number here

Are you: Male Female

What is your date of birth: //

Mobile number: What is the first half of your
postcode:

Alternative contact method (landline):

1. When did you last have an HIV test? (please tick one)

- Never
- Less than one year ago
- 1 – 2 years ago
- 2 – 5 years ago
- More than 5 years ago

2. In the last 12 months, who have you had sex with

- I have only had sex with men

- I have only had sex with women
- I have had sex with men and women
- I have not had any sex

3. In what country were you born?

Please write it down:

4. How long have you been living in the UK?

- Less than one year
- 1 – 2 years
- 2 – 5 years
- 5-10 years
- More than 10 years
- All my life

Once finished please return this to the person who is enrolling you in the Haus study.

Thank you.

Appendix 5: Acceptability Questionnaire

Please fill in this survey AFTER you have taken your sample. Thank you.

We would like to know your thoughts about this way of testing for HIV. Your answers will help us to improve this HIV testing service.

The questionnaire is confidential and takes only a couple of minutes to fill in.

1. Is it acceptable to be offered an HIV test in this manner? (circle a face below)

Acceptable      Unacceptable

2. Is it acceptable to be offered an HIV test because you are African?

Acceptable      Unacceptable

3. What did you think about the location where you were offered this kit?

Acceptable      Unacceptable

4. Did the offer of this kit help you to decide to test?

Yes No

5. Did the person who offered you the kit help you feel more confident about knowing your HIV status?

Yes No

6. Were the instructions in the kit easy to understand?

Very easy      Very difficult

7. How did you feel about taking the sample yourself?

Comfortable      Uncomfortable

Why did you feel that way? _____

8. Did you watch the online video about using this kit?

Yes

No

If yes - How did watching someone else use the kit make you feel?

Confident      Unsure

How helpful was the video?

Helpful      Unhelpful

9. How willing would you be to use one of these kits again in the future?

Very willing      Not at all willing

10. Can you tell us why you accepted this kit when it was offered to you?

11. We are very interested in your views on this service. Please tell us which aspects you particularly liked or you think we should change.

Please put this completed questionnaire in the free post envelope with your sample.

Thank you again for your time.

|

Date

Contents

GLOSSARY OF TERMS AND ABBREVIATIONS.....	65
1 INTRODUCTION.....	66
1.1 Background.....	66
1.2 Intervention Purpose	66
1.3 Intervention Process	66
1.4 Training.....	67
2 WHO IS INVOLVED IN THE STUDY	69
2.1 Overview.....	69
2.2 Core members of the study team.....	69
2.3 Extended members of the study team	69
2.4 Other Organisations Involved	70
3 MATERIALS REQUIRED AND ELIGIBILITY	70
3.1 Materials Required for GP Intervention	70
3.2 Materials Required for Community Based Organisation Intervention	71
3.3 Eligibility criteria	71
4 SCRIPTED INTERACTION	73
4.1 Aim	73
4.2 Target and Recruit.....	73
4.3 Baseline data	75
4.4 Introduce SSK.....	77
5 ANTICIPATED QUESTIONS	78
5.1 Targeting.....	78
5.2 Personal Details	78
5.3 Taking the Sample.....	79

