I agree to ensure that the confidential information contained in this document will not be used for any other purpose other than the evaluation or conduct of the clinical investigation without the prior written consent of the Sponsor.

I also confirm that I will make the findings of the study publically available through publication or other dissemination tools without any unnecessary delay and that an honest accurate and transparent account of the study will be given; and that any discrepancies from the study as planned in this protocol will be explained.

For and on behalf of the Study Sponsor:

Signature:

Date:...../...../.....

Name:

Position:

Chief Investigator:

Signature:

Date:15/02/16

Name: [name]

3. Study Summary

Short Title	The Haus Study – Phase II
Methodology	This protocol describes a prospective, mixed methods, non-randomised study to determine the feasibility and acceptability of a provider initiated, HIV self-sampling kit (SSK) distribution intervention targeted at Black Africans. The study evaluates the effectiveness of self-sampling for HIV in increasing the uptake of HIV testing by Black Africans as well as the cost effectiveness of distributing the SSK among Black Africans over other screening methods. Feasibility, acceptability and intervention fidelity will also be assessed through a process evaluation.
Research Settings	GP practices and HIV Community Based Organisations (CBO)
Research Sites	GP Practices in South London and Greater Glasgow. HIV Community based organisations in both cities.
Aims and Objectives	Overall the study aims to develop an HIV SSK intervention to increase the provision and uptake of HIV testing among Black African communities using existing community and healthcare provision. The aim of Phase II is to evaluate an HIV self-sampling kit distribution intervention targeted at Black Africans. Phase II specifically assesses the feasibility and acceptability of GP practices and community based organisations for targeted HIV SSK distribution. Phase II will inform optimal intervention design for development of a protocol for a future substantive phase III evaluation where this is deemed feasible.
2	1580 kits will be distributed to 1580 participants. 600 kits will be distributed per distributor type in London (600 by GP practice nurses and 600 by community workers) and 380 distributed in Glasgow (via primary care only).

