4.4 Risks from participating in the study

Our study does not present any elevated risks over the usual risk associated with HIV testing in standard care. It is possible that some patients may find the process of HIV testing distressing; our participant information sheet includes details of where participants can access further information and support. Participants will also have the option to ask the kit distributor if they have further questions about HIV or the SSK. Participants with a reactive result will be supported by experienced NHS staff, who are used to giving these results over the phone and supporting patients with linkage into care and support (see section 6.10 which has further details on results management). It is also possible that some people may object to and become upset at being targeted for the intervention because of their ethnicity (24). All recruiters will be provided training to ensure they are able to explain why Black African communities are being targeted and to reassure prospective participants that the intervention is intended as a health

opportunity for their community rather than a stigmatising activity. The contact details of the project manager and chief investigator are available on the patient information sheet should participants have any questions about the study.

5. Objectives and outcome measures

Hypothesis: Embedding self-sampling kits (SSKs) for HIV testing in existing services is an acceptable and feasible means to increase the provision and uptake of HIV testing among Black Africans residing in the UK.

5.1 Overall aims of phase 2

To assess feasibility, appropriateness of settings and optimal intervention design for future phase III evaluation.

5.2 Primary Objectives of Phase 2

To determine the acceptability and feasibility of a provider-initiated, HIV self-sampling kit distribution intervention targeted at Black African people in GP settings and community based HIV prevention organisations.

5.3 Secondary objectives of phase 2:

1. Determine appropriate SSK-based intervention models for GP settings and community based organisations.
2. Establish acceptability of interventions for providers and users.
3. Evaluate the effectiveness of self-sampling for HIV in increasing the uptake of HIV testing by Black African people.
4. Determine the cost effectiveness of distributing the SSKs among Black African people over other screening methods.

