5.4 Primary Outcome Measure

Our primary outcome is HIV SSK return rate.

[figure not shown]

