6.5.2 Intended Use

The ROCHE Combi assay will be used to test for the presence of HIV antibodies in participants who consent to take part in the study. The package that will be handed to participants will include:

1. The TINY kit sample collection device (including self-retracting lancets)
2. A sample data form (see appendix 7) which requires three unique sample identifiers from the participants in order for the Laboratory to be able to process the sample and to enable result notification
3. Sample collection instruction sheet (please see appendix 8). This will provide the following details:
 - Information on how to collect the sample.
 - A link to a video demonstration of collecting the sample.
 - Information on labelling the sample and postage.
 - Information on what happens after the participant posts the sample to the laboratory.
 - Information on how the result will be communicated.
 - Information on various reasons why they may be contacted by clinical team
 - A reminder about completion of the acceptability questionnaire.
4. The acceptability questionnaire (see appendix 5).
5. Stamped addressed envelope for sample and questionnaire return to the lab.

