6.8 Follow up of participants

6.8.1 Quantitative

As detailed in section 6.5.2 every kit will contain a brief acceptability questionnaire (appendix 5). The questionnaire will explore acceptability of being offered a SSK in that setting, acceptability of targeting and the process of using the kit. Each kit will come with a unique ID number, this number will be entered onto the baseline and acceptability questionnaires as well as the recruitment log, and will allow the research team to link data from the two

questionnaires with that of the test result. These data will give insight into the key features and characteristics of acceptability among those who ultimately have used the kit.

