Take your finger with the other hand and gently milk your hand and finger to help the blood drop into the blood collection tube as shown.

[figure not shown]
Fill the blood collection tube to the upper line on the side of the tube. NB: If you are unable to collect enough blood use the second lancet on another finger on the other hand. Alternatively, try wiping your finger you have been using with a dry tissue. Pause for 5-10 seconds and blood drops are likely to reform, and you can start collecting again.

Once you have filled up to the TOP FILL LINE – or even just over – stop collecting and apply the supplied spot plaster to stop the bleeding. Then push on the cap of the blood collection tube (or tubes) securely until you hear an audible click to confirm closure.

Once you have replaced the cap, gently invert the collection tube 5 to 10 times.

Make sure your tube(s) is labelled with your details using the label supplied in your pack. This is very important as unlabelled samples cannot be accepted.

Affix the label by placing the tube in the middle of the label and wrapping the label around the tube, as shown below.

Place the collection tube in the protective packing wallet provided.

Inside the self addressed, post paid mailer, please insert:

- the protective packing wallet containing the blood collection tube(s)
- used lancet(s)

Please run through the checklist below before returning samples.

CHECKLIST

Before you return your samples please tick off the contents of the white self addressed post-paid mailer.

- Completed Request form
- Blood collection tube(s) in the protective packing wallet
- Used lancets

You are now ready to seal the white self addressed post-paid mailer.

Please post your samples to The Doctors Laboratory as soon as possible from ANY Royal Mail post box in the UK. No stamp is required within the UK.

If you need assistance please contact The Doctors Laboratory on [name] or email [contact]. If you wish to return your lancets please enclose with your samples.

PLEASE TURN OVER TO FIND OUT WHAT HAPPENS NEXT

The Doctors Laboratory
[name]
[contact] [contact]
E-mail: [contact] Website: www.tdlpathology.com

Once you are finished, all you need to do is put it into a postbox, and you will usually be contacted with your results within five working days.

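### The only scaled acceptability measure among kit recipients comes from those who return a sample, about half at the planned rate, and the kit's packing checklist omits the form

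*Protocol*

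**What the plan says.** The primary objective (Protocol, section 5.2) is "To determine the acceptability and feasibility of a provider-initiated, HIV self-sampling kit distribution intervention targeted at Black African people". The primary outcome is different: "Our primary outcome is HIV SSK return rate" (section 5.4). Acceptability is a secondary outcome, worded to span takers and refusers: "Acceptability of targeted HIV SSK distribution, including rationales for accepting or refusing the offer of an SSK" (section 5.5).

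The structured instrument is the Appendix 5 questionnaire. It is packed in the kit with one reply envelope for both sample and form (section 6.5.2) and is headed "Please fill in this survey AFTER you have taken your sample". The laboratory gathers the forms that arrive with samples (section 6.9). Section 6.8.1 states what the data will describe: "acceptability among those who ultimately have used the kit".

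On prompting the user, section 6.5.2 lists among the contents of the instruction sheet (its appendix 8) "A reminder about completion of the acceptability questionnaire". The sheet as printed, which follows the Appendix 7 form, ends with a packing check: "Before you return your samples please tick off the contents of the white self addressed post-paid mailer". That checklist has three entries: the request form, the blood tube(s) and the used lancets. The insert list above it names the tube wallet and the lancets. Neither names the questionnaire.

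The planned size is given in the study summary: "1580 kits will be distributed to 1580 participants". Section 7.1 assumes a 50% return rate.

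**The concern.** Two separate matters arise.

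**Coverage.** A recipient who never posts a sample has no described route for sending the form. The scaled ratings are therefore observed only in people for whom the primary outcome was a success. Items 1 to 3 ask about the manner of the offer, being offered a test because of being African, and the place of the offer. All three can be answered as soon as the kit is handed over, yet they are put only to people who went on to use it. A percentage from this form answers the acceptability objective for returners. It does not do so for everyone who took a kit, and ratings never collected cannot be recovered by any later analysis.

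**Consistency.** The sheet that users are told to follow does not match section 6.5.2 or the form's own closing instruction to enclose it with the sample. That risks losing forms from people who did return a sample, which would be easy to avoid.

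**Working it through.** **Inputs from the protocol.** Kits: 600 (London GP) + 600 (London community) + 380 (Glasgow GP) = 1580. Return rate: 50%. Stated precision for the return rate: ±4.0% with 600 kits and ±5.0% with 380 (section 7.1).

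**Inputs not in the protocol (assumed).** Share of returners who enclose the form, q: 60% to 100%. Favourable share among returners, a_R: 90%. Favourable share among recipients without a form, a_N: 50% to 90%. The 95% confidence level is also assumed, because section 7.1 does not state one.

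**1. The plan's own figure.** Half-width = 1.96 × √(0.25/n).
- n = 600: 4.00%
- n = 380: 5.03%

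Both agree with the stated values. They describe the return rate; the protocol gives no precision for acceptability.

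**2. Coverage of the form.** c = return rate × q.
- q = 100%: 0.5 × 1580 = 790 forms at most (300, 300 and 190 by setting). Worst-case half-width is 1.96 × √(0.25/300) = 5.7% in each London setting and 1.96 × √(0.25/190) = 7.1% in Glasgow.
- q = 80%: 0.5 × 0.8 = 40% of recipients, 632 forms.
- q = 60%: 0.5 × 0.6 = 30% of recipients, 474 forms.

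**3. Bounds for all recipients with no assumption about the missing.** Lower = a_R × c; upper = a_R × c + (1 − c).
- c = 50%: 0.9 × 0.5 = 45%, up to 45% + 50% = 95%.
- c = 35% (if 70% enclose the form): 0.9 × 0.35 = 31.5%, up to 31.5% + 65% = 96.5%.

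**4. Overstatement if the returners' figure is read as covering all recipients.** Overstatement = (1 − c) × (a_R − a_N), treating returners who omit the form like non-returners.

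| a_N | c = 50% | c = 30% |
|---|---|---|
| 90% | 0 points | 0 points |
| 80% | 5 | 7 |
| 70% | 10 | 14 |
| 50% | 20 | 28 |

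The first row matters: if the two groups agree, there is no overstatement.

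**5. What each group supplies on acceptability.**
- *Recipients who return:* the scaled form, plus about 20 interviews (section 6.8.2).
- *Recipients who do not return:* about ten interviews, optional and purposively sampled (sections 6.7.3 and 6.8.2). These can explain reasons but cannot give a rate.
- *Refusers:* reason codes on the screening log (section 6.7.2 and Appendix 3), including objection to targeting and preference against self-sampling.
- *Providers:* focus groups and weekly logs (section 6.11.3, Appendix 11).

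**6. Instruction sheet against the other texts.** Section 6.5.2 promises a reminder; the extracted text of the sheet has none. Appendix 5 tells the user to enclose the form; the insert list and checklist leave it out, and the sheet then tells the user to seal the envelope. The Appendix 7 form mentions only itself and the test.

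**The case against.** The strongest reply is that the protocol has several acceptability sources and does not overclaim for this one. Refusal reasons are coded and countable. Uptake and return are behavioural indicators. The interview topic guide (Appendix 12) asks non-returners directly about being offered a test because they are African and about the location. Section 6.8.1 already confines the form to kit users. All of this stands. A reader might infer that acceptability is measured only by the form; the protocol does not support that.

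A reader might also infer that the result is biased upward. Phase 1 did record concerns about the blood kit and about perceived racism in targeting (section 4.2.1), so less favourable views among non-returners are plausible. But the protocol gives no acceptability figure for either group, and non-returners had accepted the offer and consented. The direction is not shown, and any overstatement arises only if the figure is carried beyond kit users.

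On the sheet, the form carries its own return instruction, the envelope is meant for both items, and the scripted answer on returning samples (Appendix 6, section 5.7) mentions the questionnaire. It would therefore go too far to say that users will leave it out. Figures are missing from the sheet, so the absence of a reminder is established for the extracted text only. Nor does the checklist cause the returner-only coverage; it can only reduce response among returners.

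What the reply does not remove is that recipients who accept and do not return have no structured measure, although three of the items could be put to them at hand-over. Acknowledging the limit in section 6.8.1 does not close that gap.

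**Conclusion.** The point holds as a limited measurement gap plus an internal inconsistency. Under the protocol's 50% assumption, the only scaled acceptability measure among recipients covers at most about half of them (790 of 1580), and fewer if some returners omit the form. With an illustrative 90% favourable among returners, the data alone would leave acceptability among all recipients between 45% and 95%. The size of any overstatement depends on non-returners' views, which the documents do not give; under the assumed values it runs from 0 to 20 points at 50% coverage and from 0 to 28 points at 30%. The return rate, which is the primary outcome, is unaffected. The instruction sheet conflicts with section 6.5.2 and Appendix 5 and should be reconciled with them whatever view is taken on coverage.

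**What to change.** 1. Instruction sheet: add a line for the completed acceptability questionnaire to the insert list and to the checklist, and add the reminder that section 6.5.2 promises. Cost: two lines and one sentence.
2. Baseline questionnaire (Appendix 4): copy items 1 to 3 onto it, since every participant is asked to complete it before receiving the kit. Keep them on the post-use form and report both sources. Cost: three items on a short form. The drawback is that the form is handed back to the person who made the offer, so answers may be more favourable; this should be stated with the results. Refusers would still be covered only by the reason codes.
3. Reporting: label results from the post-use form as applying to returners, and give lower and upper bounds for all recipients as in step 3 of the working. Cost: none in data collection.

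A link in the reminder texts could be added, but only as a supplement, because consent to reminders is optional (section 6.7.3) and some non-returners would not receive it.
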